### 10.4.2 ANALYSIS OF THE PRIMARY EFFICACY ENDPOINT(S)

The primary analysis will be fully pre-specified in a written SAP.

Treatment groups will be compared for the change from baseline in the ESS Total Score at Week 24 using a mixed effects analysis of covariance model for repeated measures (MMRM). The observed change from baseline score at each scheduled post-baseline visit (Weeks 4, 8, 12, 16, 20, 24, and 4 Weeks post-treatment) is the dependent variable. The model will include the baseline ESS score as a covariate, with fixed effect categorical factors for treatment group (Active and Placebo), site, visit, and the treatment  $\times$  visit interaction. The interaction remains in the model regardless of significance, and treatment group comparisons at each visit are estimated by differences of least squares (LS) means. A heterogeneous Toeplitz covariance pattern will estimate the variance-covariance of the within-subject repeated measures, and the Kenward-Roger method will be used to calculate denominator degrees of freedom. Estimates, p-values and 95% confidence intervals will be presented for treatment group comparisons at each visit. In an intent-to-treat fashion, all data will be included in the primary model, regardless of the treatment actually taken by the patient.

This model assumes missing data (such as due to a missed visit or due to early study discontinuation) is missing at random. Sensitivity analyses to this assumption to be specified in the SAP will be explored, including methods that assume that data are missing not at random, such as imputation of missing outcomes in the pomalidomide treatment group based on data from the placebo group (control-

based imputation). We will also investigate if the season of the year of enrollment is a relevant baseline covariate, given that there may be seasonal variation of epistaxis during colder months due to drier room air and increased prevalence of upper respiratory infections.

---

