**Analysis Method:** We conservatively conduct initial sample size calculations based on a T-test with equal variances (using the Power procedure within SAS). Since the primary analysis is an MMRM model with adjustment for baseline score, we next perform sensitivity power calculations which account for expected improvement in power based on the analysis plan. Data provided from the NOSE study indicated that the correlation between baseline and change from baseline at post-baseline visits is likely to be -0.4, and correlation between post-baseline visits is likely to be 0.5. Adjustment for baseline would reduce the standard deviation of the residual from 1.7 to 1.6. To evaluate power of the MMRM model in the face of increasing percent of missing data across study visits, we compute power using the formula by Lu, Luo, and Chen.

**Calculation and Sensitivity Analysis:** A total sample size of 159 patients (106 pomalidomide, 53 placebo) will provide 90% power to identify a treatment group difference in ESS change from baseline at 24 weeks of 1.0 with  $p<0.044$ , assuming a standard deviation of 1.7 and 10% early discontinuation rate. Power will remain above 80% if there is a substantially higher than expected study discontinuation rate of 30% (with 10% providing no post-baseline data): 81% based on a conservative

T-test, or 90% with the planned MMRM analysis. If the standard deviation is 1.8 instead of 1.7, the power for the planned MMRM analysis would be 91% with 10% discontinuation, and 87% with 30% discontinuation. Table 7 provides calculations for sample size selection, and Table 8 provides sensitivity of the power for the selected sample size.

Pomalidomide vs placebo Mean difference in ESS change from BL at W24	Std Dev of ESS change from BL at W24	Effect size = (mean difference) /SD	Power	Planned sample size with post-baseline data	Planned study early D/C rate	Total sample size.
-1.0	1.9	0.526	90%	180 (120:60)	10%	198 (132:66)
-1.0	1.8	0.556	90%	162 (108:54)	10%	178 (119:59)
-1.0	1.7	0.588	90%	144 (96:48)	10%	159 (106:53)
-1.0	1.6	0.625	90%	129 (86:43)	10%	141 (94:47)
-1.2	1.7	0.706	97%	144 (96:48)	10%	159 (106:53)
-0.7	1.7	0.412	62%	144 (96:48)	10%	159 (106:53)

Note: In each row, the bolded number was calculated. All other items in the row were fixed. Calculations based on a 2-sample T-test

**Table 7.** Sample size calculations for 2:1 randomization and Alpha = 0.044.

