7.7 Multiple Comparisons and Multiplicity

For inferential tests, the p-value for determination of statistical significance (Type I error) for the single primary efficacy outcome (change in ESS from baseline to week 24) will be evaluated relative to 0.044 to adjust for the interim efficacy analysis (see Section 9.6). However, the 75% interim analysis was conducted at 80% due to timing of DSMB meetings. This changed the significance level for the primary outcome from 0.044 to **0.0425** (see Appendix 3).

Significance of the treatment group comparison for 5 key secondary outcomes will be evaluated as follows: If the primary endpoint is found statistically significant at $p < 0.0425$, then the key secondary endpoints will be evaluated for statistical significance with a Hochberg modification to the Bonferroni adjustment (Hochberg, 1988), in which the p-values of the 5 outcomes will be ordered. The largest p-value will be compared relative to $p < 0.05$, and if met, all 5 endpoints will be considered significant. If not, then the second largest p-value will be assessed relative to $p < 0.05/2 = 0.025$, and if met then it and the other three endpoints will be considered significant, and so on for the third p-value compared at $0.05/3 = 0.017$, the fourth compared to $0.05/4 = 0.012$, and the fifth compared to $0.05/5 = 0.010$. Results from analyses of all other secondary endpoints and subgroup analyses will not be evaluated relative to statistical significance.

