9.3 Primary Analysis Methods

For the primary analysis, the change from baseline in epistaxis severity score after 24 weeks of study drug administration will be compared between the pomalidomide and placebo groups using a longitudinal general linear model, often referred to as a mixed model for repeated measures (MMRM) (Davis SM 2014), using the MITT population.

The observed change from baseline score at each scheduled post-baseline visit (Weeks 4, 8, 12, 16, 20, and 24 and 4-weeks post-treatment) is the dependent variable. For the purposes of this analysis, study visit will be treated as a categorical repeated measure. The model will include fixed effects for treatment group, study visit, and interactions between those variables and will include the baseline ESS score as a covariate. The model will also be adjusted for the design effect of stratification by pooled site. A heterogeneous Toeplitz covariance pattern will estimate the variance-covariance of the

within-subject repeated measures (study visit), and the Kenward-Roger method will be used to calculate denominator degrees of freedom. Estimates, p-values and 95% confidence intervals will be presented for treatment group comparisons at each visit. In an intent-to-treat fashion, all data will be included in the primary model, regardless of the treatment actually taken by the patient.

The 20 patients with 12-week post-treatment assessments will be included with all 4-week post-treatment assessments.

Treatment group comparisons of the change in ESS score averaged over the week 16, 20, and 24-week visit assessments (a secondary outcome) will be assessed via estimate and contrast statements within this model.

Sample SAS code for the primary model is as follows:

```
proc mixed covtest;
  where VISIT in ("C1","C2","C3","C4","C5","C6","EOS");
  class subject sitenum trtgp VISIT;
  model DELTA_ESS = ESS_BL sitenum trtgp VISIT trtgp*VISIT / ddfm=kenwardroger;
  repeated VISIT / subject=subject type=toeph R rcorr;
  title "Mixed model for change from baseline ESS";
  lsmeans trtgp*VISIT / cl pdiff=all;
run;
```

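### The primary MMRM fits one baseline-ESS slope to all seven visits; letting the slope vary by visit is a cheap safeguard for the week-24 comparison

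*SAP*

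**What the plan says.** The sample code in SAP 9.3 gives the fixed effects as "model DELTA_ESS = ESS_BL sitenum trtgp VISIT trtgp*VISIT". Protocol 10.4.2 agrees: "The model will include the baseline ESS score as a covariate, with fixed effect categorical factors for treatment group (Active and Placebo), site, visit", with treatment by visit as the only interaction.

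The visit factor has seven levels, C1 to C6 and EOS. EOS is off drug and mixes two timings: "The 20 patients with 12-week post-treatment assessments will be included with all 4-week post-treatment assessments". The covariance is flexible: "A heterogeneous Toeplitz covariance pattern will estimate the variance-covariance of the" repeated measures, so the variance may differ by visit. The baseline slope may not.

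No section adds a baseline-by-visit term or checks that the slope is constant. Among the sensitivity analyses in SAP 9.3.1, the only one with a slope specific to week 24 is the ANCOVA inside the multiple-imputation analyses, and these run only if the primary result is significant. Protocol 10.4.3 and SAP 9.4 carry the same model form to the QOL and (in the protocol, by name) diary outcomes. SAP 9.6 and the two interim appendices show that both interim analyses were done with the SAP 9.3 model.

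**The concern.** A single slope is an assumption about time. If regression to the mean, or a drug effect that scales with severity, builds up over the treatment period, the slope at week 24 differs from the slope at week 4. The model then adjusts the week-24 comparison with a compromise slope.

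Two things could follow. First, baseline variation that should have been removed at week 24 stays in the residual and widens the standard error. Second, if the patients who contribute week-24 data differ in baseline ESS between arms because of dropout, the compromise slope does not fully correct for that difference. The week-24 test is the sole primary test, and the five key secondary outcomes are tested only if it succeeds.

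**Working it through.** **1. The plan's own figures reproduce.** Inputs from protocol 10.5: difference 1.0, SD of change 1.7, 96:48 with data, two-sided alpha 0.044, correlation of baseline with change -0.4, correlation between visits 0.5.
- Two-sample t-test: 90.1% (stated 90%).
- Residual SD after baseline adjustment: 1.7 × √(1 - 0.4²) = 1.558 (stated as 1.6).
- MMRM at 10% dropout: 94.6%, or 93.5% with the rounded SD of 1.6 (stated 94%). At 30% dropout: 90.3% (stated 90%).

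SAP 7.7 later lowers alpha to 0.0425. In the step-2 calculation without slope error this moves power only from 94.7% to 94.5%.

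**2. First-order cost of a slope error d at week 24.** With baseline SD 1.38 (the nasal-spray trial in protocol Table 6), residual variance becomes 1.558² + (d × 1.38)². The standard error without slope error is 1.558 × √(1/96 + 1/48) = 0.275. A 1-SD chance imbalance in baseline is 1.38 × √(1/96 + 1/48) = 0.24 points and shifts the estimate by about d × 0.24.

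| d | SE increase | Power (from 94.7%) | Shift at 1-SD imbalance |
|---|---|---|---|
| 0.1 | 0.4% | 94.5% | 0.02 |
| 0.2 | 1.6% | 94.1% | 0.05 |
| 0.3 | 3.5% | 93.3% | 0.07 |
| 0.4 | 6.1% | 92.0% | 0.10 |

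**3. EOS alone.** With slope -0.70 at six visits and -0.50 at EOS, a simple average is (6 × -0.70 - 0.50)/7 = -0.67. The error at week 24 is then about 0.03, which is negligible.

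**4. Simulation, dropout unrelated to baseline.** Seven visits, 106:53, six pooled sites, REML with heterogeneous Toeplitz covariance, 600 trials per scenario, a 140-df cutoff in place of Kenward-Roger, true difference -1.00. The slope patterns are assumptions.

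| Slope over C1-C6; EOS | Dropout | SE, common v by-visit | Power, common v by-visit |
|---|---|---|---|
| -0.45 throughout | 10% | 0.278 v 0.278 | 93.7% v 93.5% |
| -0.70; -0.50 | 10% | 0.278 v 0.278 | 93.7% v 93.5% |
| -0.30 to -0.60; -0.40 | 10% | 0.281 v 0.278 | 92.8% v 93.5% |
| -0.20 to -0.70; -0.30 | 10% | 0.288 v 0.278 | 92.3% v 93.5% |
| -0.30 to -0.60; -0.40 | 30% | 0.308 v 0.304 | 85.2% v 87.5% |
| -0.20 to -0.70; -0.30 | 30% | 0.316 v 0.304 | 84.3% v 87.5% |

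The mean estimate was within 0.01 of -1.00 in every row. Simulation error is about 1 point of power near 94% and 1-2 points elsewhere. Both models were fitted to the same data sets, so the comparison within a row is the useful one. Across all simulations run, drift raised the SE by about 1-5%.

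**5. Simulation, dropout related to baseline.**
- Moderate case: slope drift, with pomalidomide dropout rising with baseline ESS. Two sets of runs put the common-slope estimate 0.03-0.07 and 0.06-0.11 points nearer zero.
- Deliberately adverse case: about 27% dropout, depending on baseline in opposite directions by arm. The common slope gave -0.84 (milder drift) and -0.74 (stronger drift) for a true -1.00; the interaction model gave -0.99. With no true effect, rejection at nominal 4.4% was 7.5% and 11.8%, against 5.5% with the interaction. The null estimates there were +0.16 and +0.26, so the excess falls against pomalidomide.
- Same adverse dropout with equal slopes: both models gave -0.99, with SE 0.295 (common) and 0.302 (by visit).

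To first order the bias is (week-24 slope - pooled slope) × (baseline difference between arms among week-24 contributors). Its direction therefore depends on the assumed pattern: reversing either factor reverses the sign.

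**The case against.** The strongest reply is that a common-slope MMRM is a legitimate prespecified choice. With dropout unrelated to baseline it is unbiased, and at the planned 10% dropout simulated power stays above the 90% target even under the stronger drift. Protocol 10.5 also reports, from the nasal-spray trial's data, one baseline-change correlation of -0.4 for the post-baseline visits, which fits a constant slope if the SD of change is constant. All of that stands, and it limits the point to a minor one.

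A reader might take protocol Table 6 as proof that the slope changes. It is not. Using slope = (SD_post² - SD_base² - SD_change²)/(2 × SD_base²), the pomalidomide pilot gives -1.30 at 12 weeks and -1.27 at 24 weeks, which is flat. The nasal-spray trial gives -0.33 at 12 weeks and -0.40 twelve weeks after stopping. The SDs do not come from the same patients: pilot baseline N=7 but change N=5; nasal-spray baseline N=120 but follow-up N=105 and 83. Differences between drugs and trials say nothing about visits within one trial.

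Two further replies are weaker. The imputation ANCOVA has its own week-24 slope, but it runs only after a significant result, so it cannot help where the common slope has weakened the effect. It also changes the missing-data assumption. The use of the SAP 9.3 model at both interims is a real but small drawback: SAP 9.2 and 9.4 already record other changes made at masked data review, including replacing the transfusion amount with a yes/no outcome.

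**Conclusion.** The model does impose one baseline slope on C1-C6 and EOS, and no unconditional analysis relaxes it. The likely cost is small: about 1-5% in the week-24 standard error if the slope drifts over C1-C6, worth roughly 1 point of power at 10% dropout and 2-3 points at 30%. Bias needs two conditions together, slope drift and dropout that depends on baseline differently by arm. In moderate assumed scenarios it is about 0.03-0.11 points towards zero.

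Three stronger conclusions are not supported:
- The primary analysis is not invalid. Randomization protects it unless dropout is selective on baseline.
- The off-drug EOS visit does not by itself distort week 24. Drift across C1-C6 is what matters.
- The type I error figures of 7.5% and 11.8% illustrate an adverse dropout pattern that nothing in the documents suggests.

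All drift and dropout patterns above are assumptions; the documents neither show nor exclude them. Importance is low, and the case for change rests on its small cost.

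**What to change.** Before unblinding, masked staff who have not seen the interim results should:
- add `ESS_BL*VISIT` to the MODEL statement in SAP 9.3, giving one baseline slope per visit, and keep the week-24 LS-means contrast as the primary test;
- use the same form in the QOL and diary MMRMs;
- record the change in SAP 12, which now states that nothing differs from the protocol, and note there that both interims used the common-slope model;
- report the common-slope model as a sensitivity analysis.

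If the primary model can no longer be changed, run the interaction model as a sensitivity analysis whatever the primary result.

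The cost is 6 degrees of freedom out of at most 7 × 159 = 1,113 repeated observations, and 2 in the three-timepoint QOL and diary models. With equal slopes and dropout unrelated to baseline, the standard error is essentially unchanged. Under the adverse dropout pattern with equal slopes it rises by about 2% (0.302 v 0.295). The main drawback is that the final model differs slightly from the one used at the interims.

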9.3.1 Sensitivity Analyses

Per-protocol population

The primary analysis will be repeated on the per-protocol population.

Imbalanced covariates

If there are important baseline characteristics that substantially differ between randomized treatment groups by chance, additional sensitivity analyses may be conducted to evaluate the impact of adjusting for those imbalances.

Clinical Site Effects

We will examine descriptively whether the treatment effect varies across sites.

Removing 12-week post-treatment data

A supportive analysis of the 4-week post-treatment assessment time will be completed for the MITT population with removal of the 20 patient visits that were conducted at 12 weeks post-treatment.

Missing data

The MMRM analysis approach assumes missing data due to missed visits or early study discontinuations are missing at random (MAR). If a statistically significant difference between treatment groups is observed in the primary analysis, then a sensitivity analysis will be conducted on the primary outcome to assess the robustness of the primary analysis to the MAR assumption using methods that assume that data are missing not at random (MNAR). Specifically, we will use multiple imputation of missing data to generate multiple imputed complete datasets (no missing data through 24 weeks), conduct analysis of covariance for change from baseline at 24 weeks on each dataset (model change from baseline at 24 weeks = baseline value + site + treatment group), and use Rubin's rule to combine results across the imputed datasets to obtain a comparison of treatment groups (Ratitch, 2014). We will explore 2 sensitivity analyses: (a) impute missing outcomes in the

pomalidomide treatment group (and the placebo group) based on data from the placebo group (control-based imputation), and (b) impute missing outcomes in the pomalidomide group at varying percentages of the observed values (while imputing missing placebo data based on observed placebo values) until a statistically significant treatment group difference is no longer identified (tipping point analysis) (O'Kelly and Ratitch, 2014). These sensitivity analyses will only be conducted if the primary analysis identifies a statistically significant treatment group difference at 24 weeks in the MITT population.

Intercurrent concomitant therapy

It is possible that participants in either treatment group may receive concomitant therapy that might impact the ESS score. For example, receiving an RBC transfusion would likely improve the anemia status; however, in this case the ESS score would have extra points for seeking medical care and receiving an RBC transfusion. Therefore, based on the ESS scoring weights, receiving an RBC transfusion would appropriately make the ESS score worse (higher score) in the month it is received. Iron infusions may also impact the anemia score, in which case there might be an extra ESS point for seeking the medical attention to obtain the iron infusion, thereby a slightly negative impact on the ESS score. On the other hand, nasal cauterization or other endoscopic intervention may impact bleeding and therefore might impact the ESS score to indicate improved ESS due to the endoscopic treatment.

If applicable, we will descriptively evaluate the amount and timing of iron infusions and endoscopic interventions such as nasal cauterization. If there are a substantial number of these events, we may descriptively evaluate if these events seem to have an impact on improving the ESS score, and if so, consider a sensitivity analysis of the impact of the intercurrent treatments on the primary treatment group comparisons. We will do this evaluation only if warranted by evaluation of the number of intercurrent events within the treatment groups.

Pre-specified Covariates/Subgroup analyses

We will investigate the primary outcome analysis for the MITT population on the pre-planned subgroups specified in the protocol: genetic confirmation of HHT (yes or no), gender and race (per NIH guidelines).

We will also investigate interactions for type of genetic mutation, and if the season of the year of enrollment is a relevant baseline covariate, given that there may be seasonal variation of epistaxis during colder months due to drier room air and increased prevalence of upper respiratory infections.

Interactions will be assessed within the primary mixed linear model by adding an interaction term between treatment group and subgroup and evaluating this multiple degree of freedom test at the 0.10 significance level, and if trends are identified then graphing the trajectories over time by subgroup, using a model with the treatment group x time x subgroup 3-way interaction.

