6 SAMPLE SIZE DETERMINATION

We anticipate consenting up to 200 participants to reach 159 randomized participants.

A total sample size of 159 patients (106 pomalidomide, 53 placebo) will provide 94% power to identify a treatment group difference in ESS change from baseline at 24 weeks of 1.0 with $p<0.044$ (per interim analysis alpha spending rules), assuming a standard deviation of 1.7 and 10% early discontinuation rate with the planned MMRM analysis. Power will remain above 80% if there is a substantially higher than expected study discontinuation rate of 30% (with 10% providing no post-baseline data): 81% based on a conservative T-test, or 90% with the planned MMRM analysis. If the standard deviation is 1.8 instead of 1.7, the power for the planned MMRM analysis would be 91% with 10% discontinuation, and 87% with 30% discontinuation.

With 159 patients, we will also have at least 90% power to identify a treatment group difference of 30% for a binary secondary endpoint of proportion of participants requiring at least one packed red blood cell transfusion or iron infusion at any time during the 24-week treatment period with $p < 0.05$, whether assuming a rate in the placebo and pomalidomide groups of 90% vs. 60%, or 50% vs. 20%.

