7 STATISTICAL/ANALYTICAL ISSUES

7.1 General Rules

All statistical computations will be performed, and data summaries created using SAS 9.4 or higher. For summaries of study data, categorical measures will be summarized in tables listing the frequency and the percentage of subjects in each study arm; continuous data will be summarized by presenting mean, standard deviation, median and range; and ordinal data will be summarized by presenting median and range.

Estimates from linear models will be presented by mean, standard error, and 95% CI. Estimates from logistic regression will be presented by odds ratios and 95% CIs. All statistical tests will be 2-tailed.

Checks of assumptions (e.g., normality) underlying statistical procedures will be performed and corrective procedures such as use of a transformation or application of nonparametric tests will be applied.

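### The tipping-point analysis scales imputed pomalidomide outcomes by an undefined percentage; on its most direct reading this shrinks their variance and tips modestly later than an additive shift

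*SAP*

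**What the plan says.** SAP 9.3.1 (Missing data) plans two missing-not-at-random analyses, run only if the primary comparison is significant. Both use multiple imputation, an ANCOVA at week 24 ("model change from baseline at 24 weeks = baseline value + site + treatment group") and Rubin's rule.

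- Analysis (a) imputes both arms "based on data from the placebo group (control-based imputation").
- Analysis (b), the tipping point, is to "impute missing outcomes in the pomalidomide group at varying percentages of the observed values". Gaps in the placebo arm are filled from that arm's own data, without any scaling. The search goes on "until a statistically significant treatment group difference is no longer identified".

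SAP 9.2 defines the primary outcome as the difference between the ESS at a visit and the ESS at baseline, so negative values are improvement. The SAP does not say whether the percentage applies to each imputed draw or to the mean, or to the change or the ESS itself. It gives no grid, floor or ceiling. The significance level that decides when the result has tipped is in SAP 7.7: "This changed the significance level for the primary outcome from 0.044 to 0.0425".

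**The concern.** A change score has a meaningful zero and takes both signs, so multiplying it is not a uniform penalty. At 50%, an imputed improvement is halved, but so are an imputed worsening and the spread of all imputed values. A stress test should not gain precision as its assumption becomes harsher.

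A percentage is also hard to interpret. If the pomalidomide mean is -2.5, 50% means 1.25 ESS points of worsening; if it is -1.5, 50% means 0.75. The size of the penalty therefore depends on the observed mean, including whatever part of it is placebo-type response.

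Missing week-24 data could be appreciable. Protocol 7.3.5 sends a patient who stops drug permanently to the current cycle visit and one further visit four weeks later, so most who stop before cycle 6 would have no week-24 ESS. Protocol Table 6 records 2 of 9 pilot patients (22%) lost to rash, and SAP section 6 examines 30% discontinuation. Because analysis (b) runs only after a significant primary result, the choice between readings would be made with that result known.

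**Working it through.** **1. The plan's own figure.** The documents give no figure for the tipping-point analysis, so the design power was reproduced to confirm the inputs. Protocol 10.5: 96:48 evaluable, difference 1.0, SD 1.7, two-sided 0.044.

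- SE = 1.7 × √(1/96 + 1/48) = 0.3005; 1.0/0.3005 = 3.328.
- Critical z = 2.014; Φ(3.328 − 2.014) = 90.6%; noncentral t gives 90.1%. Stated: 90%.
- With 30% discontinuation: 81.1%. Stated: 81%.

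**2. Algebra.** Let an imputed change have mean μ and SD σ.

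- Scaling: kY has mean kμ and variance k²σ². At k = 0.5 and σ = 1.7 the SD falls to 0.85; at k = 0 it is zero.
- Shift with the same mean: Y + (k − 1)μ has mean kμ and variance σ².
- Share of draws above zero (worsening) at SD 1.7: Φ(−2.5/1.7) = 7% at mean −2.5; Φ(−2.7/1.7) = 6% at −2.7; Φ(−1.5/1.7) = 19% at −1.5. With μ = −2.5 and k = 0.5, a draw of +1.0 becomes +0.5 under scaling and +2.25 under the shift. The average imputed value gets worse by the same amount under both.

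**3. Simulation.** Inputs from Protocol 10.5: 106:53, SD 1.7, correlation −0.4 between baseline and change, baseline SD 1.38 (Table 6), placebo mean −1.5, pomalidomide mean −2.5 (placebo plus the planned 1.0). Missing fractions of 10% and 30% are from SAP section 6; applying them equally to both arms is an assumption. Method: regression imputation within arm under missing at random, 20 imputations, ANCOVA on change adjusted for baseline (site omitted), Rubin's rule, critical z 2.0286 (SAP Appendix 3), 150 trials per scenario. Scaling and shift use the same draws.

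| Missing | k | SE scaled | SE shifted | Mean z scaled | Mean z shifted |
|---|---|---|---|---|---|
| 10% | 0.50 | 0.271 | 0.281 | −3.32 | −3.20 |
| 10% | 0 | 0.284 | 0.296 | −2.71 | −2.60 |
| 30% | 1.00 | 0.319 | 0.319 | −3.05 | −3.05 |
| 30% | 0.75 | 0.305 | 0.322 | −2.58 | −2.44 |
| 30% | 0.50 | 0.300 | 0.329 | −1.99 | −1.82 |
| 30% | 0.25 | 0.306 | 0.341 | −1.33 | −1.20 |
| 30% | 0 | 0.323 | 0.356 | −0.68 | −0.62 |

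With 30% missing, the scaled SE falls from 0.319 to 0.300 as the assumption hardens to 50%; the shifted SE only rises.

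SE reduction, scaled against shifted:

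- 10% missing: 1 − 0.271/0.281 = 3.6% at k = 0.5 and 1 − 0.284/0.296 = 4.1% at k = 0.
- 30% missing: 1 − 0.300/0.329 = 8.8% and 1 − 0.323/0.356 = 9.3%. Over the other arm means tried (−2.7/−1.5, −1.5/−0.5, −1.0/0) and k from 0.5 to 0, it runs from 8.5% (0.302 against 0.330) to 11.7% (0.293 against 0.332).

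**4. Tipping point, 30% missing**, interpolating mean z to −2.0286:

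- Scaled: k = 0.75 − 0.25 × (2.58 − 2.0286)/(2.58 − 1.99) = 0.52; worsening (1 − 0.52) × 2.5 = 1.2 points.
- Shifted: k = 0.75 − 0.25 × (2.44 − 2.0286)/(2.44 − 1.82) = 0.58; worsening (1 − 0.58) × 2.5 = 1.0 point.

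**5. Trials still significant.** At 50% with 30% missing: 47% scaled against 35% shifted in this run, and 47% against 42% in a second run, so the gap is best read as 5 to 12 percentage points. Of trials significant under missing at random, those still significant at 0%, scaled against shifted:

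| Arm means | Missing | Scaled | Shifted |
|---|---|---|---|
| −2.5/−1.5 | 10% | 84% | 81% |
| −2.5/−1.5 | 30% | 7% | 4% |
| −1.5/−0.5 | 30% | 57% | 44% |
| −1.0/0 | 30% | 76% | 62% |

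Each percentage carries up to about 4 points of simulation standard error; the paired contrasts are more precise.

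**The case against.** The strongest reply is that draw-by-draw scaling is only one reading. If the percentage sets the mean and residual variation is then added, the variance is kept and worsenings are not pulled in. If it applies to the ESS itself and exceeds 100%, the variance grows. This stands: the variance loss is a property of one reading, though the most direct one given how the outcome is defined.

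A reader might also infer that the analysis cannot tip, or that patients who got worse are never represented. The documents do not support that. It needs a floor at 0%, which the SAP does not set; it says to continue until significance is lost. With means −2.5/−1.5 and 30% missing, about nine in ten significant trials tip before 0% even when scaled. With 10% missing most do not, but an equal shift gives nearly the same answer (84% against 81%), so the cause is the small missing fraction. And 0% already places pomalidomide dropouts 1.5 points worse than a placebo mean of −1.5, about twice the 0.7 minimal important difference.

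Nor do the documents support a claim that the plan is strongly biased towards calling the result robust. Section 9.3.1 sets no robustness threshold, and the control-based analysis is a separate check without this feature.

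**Conclusion.** The concern holds in a limited form. The percentage rule is under-specified. If each imputed change is multiplied, the analysis loses variance and tips modestly later: a standard error about 4% lower with 10% missing and about 8 to 12% lower with 30% missing, and, for means −2.5/−1.5 with 30% missing, a tipping point near 1.2 rather than 1.0 ESS points. That difference of about 0.2 is small beside the planned 1.0, but not negligible beside the 0.7 minimal important difference. At about 10% missing the two methods practically agree.

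These sizes rest on draw-by-draw scaling, equal missingness in both arms, normal imputation, and a model of week 24 alone. The −1.5/−0.5 and −1.0/0 arm means are illustrative. The primary analysis and the control-based analysis are untouched.

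**What to change.** Replace the percentage rule in SAP 9.3.1(b), before unmasking, with an additive delta:

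- impute week-24 change under missing at random in both arms;
- add the same constant delta (towards worsening) to every imputed pomalidomide change, leaving imputed placebo values as they are;
- raise delta over a range and step stated in advance until the two-sided p-value is at least 0.0425; if it never is, report that together with the top of the range;
- report the tipping delta in ESS points beside the 0.7 minimal important difference and the planned 1.0.

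This keeps the imputed variance, penalises every imputed value equally and gives a result clinicians can judge directly. It costs one sentence of SAP text. The only downside is a tipping point that may look slightly less favourable.
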